# 5.4 Withdrawal/Discontinuation

# 5.4.1 Withdrawal conditions

The volunteers have the right to withdraw from the trial at any time and for any reason. The researcher has a right to withdraw persons in case of occurrence of inter-current diseases, adverse reactions and the persons committing gross violation of the trial rules, for administrative or any other reasons, eg. lost to follow up, move from study area, in jail etc.

All interested parties understand, that excessive number of withdrawals can result in improper interpretation of the trial results, therefore it is necessary to avoid unreasonable decisions. It is necessary to avoid withdrawals, nevertheless, we understand, that they can take place during the trial. However, irrespective of the volunteer withdrawal period and reason, the final assessment of the trial concerning these participants should be made. The decision to withdraw a volunteer in VED connection to absence at the trial procedures should be made by the researcher only after finding-out of all circumstances. Given these factors and the importance of collecting full safety data from MITTEE FACULTY OF TROPICAL MEDICINE

MAHIDOL UNIVERSITY

ัดยาลัยมั้

all participants, the reasons for terminating from the study should be minimal, but may include the following:

- Participant withdraws consent.
- PI decides that termination is in the best interest of the participant.
- The sponsor terminates the study.
- The targeted number of participants has been reached.

The decision to withdraw a volunteer in connection to presence of intercurrent disease or adverse reactions should be documented in the case record forms.

# 5.4.2 Procedure for Withdrawal/Discontinuation volunteer

The investigator or study coordinator must notify the SPONSOR and to the WHO focal point immediately when a participant has been discontinued/ withdrawn due to an adverse experience (email or telephone or FAX). When a subject discontinues/withdraws prior to study completion, all applicable activities scheduled for the final study visit should be performed at the time of discontinuation. experiences which Any adverse are present at the time of discontinuation/withdrawal should be followed in accordance with the safety requirements.

Note: For participants who discontinue/withdraw prior to completion of the last visit, final visit procedures will be applied.

#### 5.4.3 Procedure of replacement of the withdrawn volunteer

No replacement plan for this study.

# 5.4.4 Strategies to Maintain and Recruit Additional Participants

This is a relatively short trial with only one injection and 4 planned study visits per participant. Strategies to maintain retention in the trial include treating them respectfully, making sure they understand the study and potential side effects, and close communication with each participant about how the study unfolds. Given the short duration of the trial and anticipated minimal side effects of the study vaccine, participant withdrawal and loss of follow-up is expected to be low.

#### 5.5 Lost to follow up

In the case of subjects who fail to return for a follow-up visit, documented reasonable efforts (i.e., documented telephone calls or certified mail) should be undertaken to locate or recall them, or at least to determine their health status while fully respecting their rights. These efforts should be documented in the source documents and CRF.

# 6. Termination of the Trial

# 6.1 End of Trial According to the Protocol

The end of the trial is defined as the date of the last contact of the last participant participating in the trial, according to the trial scheme.

# 6.2 Suspension and/or Premature Termination of the Trial

The trial may be prematurely terminated if the subject experienced disability or severe adverse event or death and such event is definitely related to study vaccine in the investigator's opinion.MMITTEE Furthermore, the Data Safety Monitoring Board (DSMB) judge to retruinate the trial. The trialCAL MEDICINE MAHIDOL UNIVERSITY

US C

might be suspended at any time by GPO or the Thai FDA, any ethical review committee overseeing this study (for that institution only), or by the investigator (for his or her site only) for any safety concern. This includes, for example, and without limitation, an SAE resulting in death or an unusually high rate of SAEs. The Sponsor can terminate the trial for any reason which may not relate to safety of the volunteers. However, volunteers will be continued to follow for safety.

In the event of new data that indicate an increased level of risk to enrolled participants, the clinical trial will be suspended until GPO, the Thai FDA and all ethical review committees have reviewed relevant data and agreed that the trial may continue.

# 7. Study Schedule; Description of Visits

#### 7.1 Recruitment

After getting approval from the Ethic Committee and before the start of the trial, the study team will inform the interested subjects about the study by word of mouth from existing pool of volunteers or through the recruitment materials which have been approved by Ethics Committee prior to use which will be distributed in the community health campaign.

A contact address and phone number will be provided for the interested subjects to call for more information about the study. Subjects who are interested in participating will be scheduled for a formal briefing and the informed consent process. The interested subjects will present at the clinical site on the day assigned. The clinical site will also accommodate "walk-ins".

Prior to inclusion into the vaccine study, each participant will undergo medical history interview and general physical examination. Because screening procedures are required to assess eligibility, they will be performed only after consent is obtained. The Principal Investigator or designee will record the identity (IDs) of all participants who enter screening; whether they entered the trial or failed screening, and the reason for screen failure will be recorded on the screening/enrollment log.

#### 7.2 Study Visits: Screening Visit

Screening: At the screening visit, prior to perform any study specific procedures, the Investigator and/or designated staff must provide all information related to the study to the subjects. Subjects must have enough time to read the Informed Consent Forms which have been approved by an Ethics Committee and ask questions. If the subjects are interested to participate in the study, they shall sign and date in the Informed Consent Form thereafter. The investigator or delegate who involves in the consent process shall check the completion of the consent forms and then sign and date on the same day of signing by the subject. A copy of the signed informed consent form will be given to each participant for his/her records.

After signing of informed consent form, all subjects will be screened for eligibility through medical history review and physical examination. All volunteers will be checked against the inclusion/exclusion criteria.

The screening assessments will be performed up to 30 days prior to the first vaccination.

The screening procedures for the study included a medical history, vital signs, and physical examination will be performed. A urine pregnancy test will be done in females. Female volunteers should avoid pregnancy at least 60 days after the vaccination by using an effective birth control method. They will be provided pregnancy counseling and the contraceptive pills or injection will be VED offered for free. Participants who meet eligibility criteria will be enrolled. 3 ml blood samples will be collected prior to vaccination.

MAHIDOL UNIVERSITY

ตยาลัยม

7.3 Vaccination (can be the same day as screening day): A single dose of a seasonal trivalent inactivated split virion influenza vaccine [A/Michigan/45/2015 (H1N1) pdm09-like virus, A/Hong Kong/4801/2014 (H3N2)-like virus, and B/Brisbane/60/2008-like virus] in GPO Tri Fluvac and comparator will be given to all subjects after blood collection for immunology assays. The vaccine will be administered via the intramuscular route; the preferred injection site will be the deltoid of the non-dominant arm. After vaccination volunteers will remain at the clinic for at least 30 minutes to observe for any reactogenicity after immunization. A diary card will be provided to the subjects for recording such events for 3 days after vaccination (Day 1-3).

At this visit; Repeat urine pregnancy tests will be performed if the immunization day is not the same as the screening day

- 1. The participant will be asked to complete the dairy card for 3 days, starting in the next day after injection, reporting any local or systemic reactions experienced and medications taken. The record of reactogenicity at 30 minute after immunization will be done at the clinical site.
- 2. The participant will have been instructed that if he/she experiences an AE requiring medical care, the participant should inform the investigator as soon as possible and seek medical care as appropriate. If the participant visits a health care provider, the participant should be sure to inform the health care provider of participation in this study and provide the health care provider with the investigator's contact information. The participant should obtain in writing the names of medications prescribed by the health care provider.

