# **Primary Safety Endpoints:**

The number and proportion of participants reporting the following events will be assessed:

- Solicited local adverse events, including redness / erythema, swelling / induration, pain, and limitation of arm movement within 30 minutes of vaccination and over the 3-day period post-vaccination (Days 0-3).
- Solicited systemic adverse events, including fever, fatigue/malaise, muscle aches, joint aches, chills, nausea, and headache within 30 minutes of vaccination and over the 3-day period post-vaccination (Day 0-3).
- Unsolicited Adverse Events (AEs) occurring within 90 days post-vaccination.
- Serious Adverse Events (SAE) occurring during the entire study period (Days 0-90).

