# 4. STUDY DESIGN:

# 4.1 Study Design

This is a phase II/III, non-inferiority double-blinded, randomized, and controlled trial to evaluate the safety and immunogenicity of a single dose the GPO seasonal trivalent inactivated influenza vaccine in male and female adults, ages 18 to 49 years old. Participants will be randomized 2:1 to one of two treatment allocations: 630 to vaccine, 315 to comparator. The study will be double blinded, meaning the study participants, investigators, and the sponsor will be unaware of the treatment allocated to each participant until the clinical trial database is declared final and locked.

All participants will be consented for participation and screened for eligibility through medical history review and physical examination. All volunteers will be checked against the inclusion/exclusion criteria. The screening assessments will be performed up to 30 days prior to the first vaccination. The screening procedures for the study including a medical history, vital signs, and physical examination will be performed. A urine pregnancy test will be done in females on screening day, day 0 prior to vaccination. Female volunteers should avoid pregnancy from the screening visit until at least 60 days after the vaccination by using an effective birth control method. The baseline immune response will be performed on day 0 prior to vaccination. One dose of the investigational vaccine or comparator will be given by intramuscular route (preferred injection site will be the deltoid of the non-dominant arm) after blood collection for immunology assays. Total follow-up period is 90 days for immune response and safety.

There will be 4 clinical visits and 1 phone visit as follows:

- Screening Visit (Day -30 to Day 0) Sign informed consent form, screen for eligibility (medical history review and physical examination)
- Day 0 (can be the same day with screening day): Vaccination day, subjects will remain at the clinic for at least 30 minutes for observation of any reactogenicity after vaccination. A diary card will be provided to the subjects for recording such events for 3 days after vaccination (Day 0-3).
- Day 7 (-3, + 7days): Return the diary card and report any adverse events that occur during the first seven days after immunization. Concomitant medication information will be collected.
- Day 21 (+7 days): Blood specimen collection for immune response, follow-up and report VEI any adverse events.

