## Table 2: Study Schedule and activities

Procedures	Study Day						
		D0	D7	D21	D60	D90	
			(-3, +7)	(+7)	(+14)	(+7)	
	Screening e	Immunization e					
Informed consent	X						
Assessment of entry criteria	Х	(X) f					
Medical history, AE/SAE, Concomitant medication	Х	(X) f	X	Х	Х	Х	
Vital signs	Х	(X) f	Х	Х		Х	
Urine pregnancy test a	Х	(X) f					
Physical examination a	Х	(X)	(X)	(X)		(X)	
Immunization		X					
Diary card b		X (Day 0-3)	X				
Blood for Immune response (HI Assay) (3ml)		X		Х		Х	
Phone call visit c					Х		
Influenza subtype by RT- PCR d			(X)	(X)	(X)	(X)	

Remark

a. Only at screening, the rest when the history suggested [(x) = Optional as indicated by medical history].

b. Diary card will be provided to the subjects for recording reactogenicity for 3 days after vaccination (Day 0-3) and return to review at Day 7.

c. At Day 60, adverse events and influenza-like illness (ILI) will be followed-up by phone call.

d. Determination of influenza subtype by RT-PCR will be done when the ILI is confirmed [(x) = Optional as indicated].

e. Screening day can be the same day as immunization day (D0)

f. Will be done if immunization is not performed on screening day

(x) Optional

ETHICS COMMITTEE FACULTY OF TROPICAL MEDICINE MAHIDOL UNIVERSITY

APPROVED

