# 8. SAFETY AND LABORATORY EVALUATIONS

## 8.1 Safety Evaluations

All adverse experiences will be collected after the immunization throughout the period of the study. Such events will be recorded at each examination on the Adverse Experience Case Report Forms/Worksheets. Serious adverse experiences will also be collected and reported.

- Immediate reactions occurring within 30 minutes of vaccine administration
- Commonly occurring adverse events associated with vaccination, i.e., solicited adverse symptoms recorded during days 1-3.

• All other adverse events (including unsolicited events) occurring throughout the period of the study

An adverse experience is defined as any unfavorable and unintended change in the structure, function, or chemistry of the body temporally associated with the use of vaccine, whether or not considered related to the use of the product. Any worsening (i.e. any clinically significant adverse change in frequency and/or intensity) of a preexisting condition, which is temporally associated with the use of the vaccine, is also an adverse experience. The occurrence of an AE might come to the attention of study personnel during study visits and interviews of a study participant presenting for medical care. Information to be collected on AEs includes event description, time of onset, clinician's assessment of severity, relationship to study product, and time of resolution/stabilization of the event. AE assessment should be made only by those with the training and authority to make a diagnosis. Any medical condition that was present at the time that the participant was enrolled should not be reported as an AE, but should be reported as a pre-existing condition on the Medical VED History Form. However, if this condition occurs with greater frequency or severity during the study, it should be recorded as an AE

Protocol: GPO Tri Fluvac Vaccine Phase II/III\_ Version 3.1 dated 13 Mar 2017

MAHIDOL UNIVERSITY

ไตยาลัยม

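### The solicited-reaction window contradicts itself: Day 0-3 in the endpoint, Day 1-3 in the diary instruction, and no SAP slot for Day 0 after 30 minutes

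*Protocol*

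**What the plan says.** Two windows stand in the Protocol.

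**Day 0-3.** The Primary Safety Endpoints in Protocol Section 3 count solicited local reactions within 30 minutes and "over the 3-day period post-vaccination (Days 0-3". The systemic item has the same window, as do the Protocol Summary, Sections 11.3.2 and 11.4, and the SAP synopsis. Section 4.1 matches this for data collection: "A diary card will be provided to the subjects for recording such events for 3 days after vaccination (Day 0-3". In Table 2 the D0 column marks the diary as Day 0-3, and remark b describes the card as being for "recording reactogenicity for 3 days after vaccination (Day 0-3) and return to review at Day 7".

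**Day 1-3.** Section 7.3 (Vaccination) says that the card is for "recording such events for 3 days after vaccination (Day 1-3". Its first numbered instruction has the participant complete the card for three days, "starting in the next day after injection, reporting any local or systemic reactions experienced and medications taken". The only Day 0 record it names is made by the site: "The record of reactogenicity at 30 minute after immunization will be done at the clinical site". Section 8.1 lists "solicited adverse symptoms recorded during days 1-3" alongside immediate reactions within 30 minutes.

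Sections 8.2 and 8.5 describe a check at 30 minutes followed by daily recording for three days, which fits either reading. SAP shells TREF 3.2 (temperature), TREF 3.6 (local reactions) and TREF 3.11 (systemic reactions) are laid out by 30 min, Day 1, Day 2 and Day 3.

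**The concern.** An endpoint defined over Day 0-3 needs data for all of Day 0. Under the Section 7.3 instruction, the hours between leaving the clinic and the next day belong to the endpoint, but the participant is not told to record them and the by-time tables have nowhere to put them.

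Solicited reactions are a primary safety endpoint. Section 11.4 compares their percentages between arms at a two-sided 0.05 level, and the stopping rules in Section 9.3 count participants with grade 3 or greater reactogenicity. Both depend on complete capture over the stated window. The diary method is prospective: Section 8.2 supplies a thermometer, a ruler and severity grading. An oral temperature or a diameter in centimetres that was not measured on the evening of Day 0 cannot be measured later.

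**Working it through.** The plan states no figure for this point, so the check is a comparison of passages, followed by what each reading would capture.

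**1. Windows side by side**

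| Place | Window | Day 0 after 30 min |
|---|---|---|
| Protocol Summary; Sections 3, 11.3.2, 11.4; SAP synopsis (endpoint) | 30 min and Day 0-3 | inside |
| Protocol 4.1; Table 2 and remark b (diary) | Day 0-3 | inside |
| Protocol 7.3, narrative and instruction 1 (diary) | Day 1-3, from the next day | outside |
| Protocol 8.1 (solicited symptoms) | 30 min and days 1-3 | outside |
| Protocol 8.2, 8.5 | 30 min, then daily for three days | not settled |
| SAP TREF 3.2, 3.6, 3.11 | 30 min, Day 1, 2, 3 | no slot |

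Day 0-3 is 4 calendar days. Section 7.3 and the three shells provide 3 diary days plus the 30-minute check. TREF 3.8 (number of days with a local reaction) also stops at 3 days. TREF 3.1 does have a Day 0 row, but its rows (Day 0, 7, 21, 90) are clinic visits at which Table 2 schedules vital signs, so it does not hold the evening of Day 0.

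**2. What is captured if Section 7.3 and the shells are followed**

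- Present at the 30-minute check: recorded by site staff.
- Starts after 30 minutes and is still present at the Day 1 entry: recorded on Day 1.
- Starts after 30 minutes and resolves before the Day 1 entry: no prospective graded record. Only this group is at risk.

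**3. Effect on the rates**

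Let p be the proportion of participants with a given solicited reaction over Day 0-3, and f the fraction of them whose only episode is of the third kind and is not recovered.

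- Reported rate: p × (1 − f), which is below p whenever f > 0.
- Between-arm difference with the same f in both arms: (pT − pC) × (1 − f), so it shrinks.
- Between-arm ratio with the same f: pT(1 − f) / [pC(1 − f)] = pT/pC, unchanged.
- With different f in each arm, the direction is not known.

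Neither document gives f or anything from which to derive it.

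**4. Length of the gap, for orientation only**

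The documents give no time of vaccination. Assume 08:00 to 16:00.

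- From 30 minutes after injection to midnight: 24 − 8 − 0.5 = 15.5 h, down to 24 − 16 − 0.5 = 7.5 h.
- From injection to the end of Day 3: (24 − 8) + 72 = 88 h, or (24 − 16) + 72 = 80 h.
- Share of that time: 15.5/88 = 17.6%, or 7.5/80 = 9.4%.

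This is a share of clock time. It is not an estimate of f.

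**The case against.** The strongest reply is that the gap may not exist in practice. Section 4.1 and Table 2 put the diary at Day 0-3, and nothing ranks Section 7.3 above them. Section 4.6.3 has the card, ruler and thermometer handed over and explained on Day 0. The Section 7.3 instruction says when the card is filled in and does not confine the first entry to symptoms that began on Day 1. The diary card itself is not in the documents, so its recall interval cannot be checked. Section 8.3 makes a solicited-type symptom unsolicited only if it starts after three days, so a Day 0 onset is solicited by definition. At Day 7 staff review the diary and interim history and ask about any adverse event in the first seven days, and Section 8.5 reports safety events from injection.

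The SAP shells are also imperfect evidence of the collection window. Their labels may be assessment times rather than onset intervals, TREF 3.13 allows systemic reactions of 4 and 5 days, which fits neither window, and the maximum-grade tables TREF 3.5, 3.7 and 3.12 are over any day and would include Day 0 entries if these were collected.

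Most of this stands. It rules out saying that the diary simply starts on Day 1. It does not remove the contradiction: a site following Section 7.3 and a site following Table 2 would collect different data under the same protocol. Nor is Day 7 an equivalent safeguard. With its −3/+7 day window it falls anywhere from Day 4 to Day 14, it relies on memory, and Section 7.4.1 sends to the CRF only adverse events that reach a reporting intensity.

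**Conclusion.** The contradiction is certain from the text. The loss of data is conditional: it follows if Section 7.3 and the SAP shells, rather than Section 4.1 and Table 2, governed what was recorded. In that case reactions confined to the interval between the 30-minute check and the Day 1 entry would not be captured prospectively as graded solicited events, and solicited rates for the stated Day 0-3 endpoint would be understated in both arms. The documents do not allow the size to be estimated.

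Three stronger conclusions are tempting and are not supported.

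- A reader might infer that Day 0 reactions after 30 minutes are never recorded. Those that persist into Day 1 are recorded, Day 7 recall may recover others, and part of the Protocol does set the diary at Day 0-3.
- A reader might take the 32.5% pain rate in the phase I/II vaccine group and discount it by an assumed share of same-day pain. No such share is given, some same-day pain would be noted at 30 minutes, and the diary window of that trial is not stated. Section 2.6 expects systemic symptoms to clear within 1-3 days, which does not point to widespread same-day resolution.
- A reader might infer bias towards one vaccine. The procedure is the same in both blinded arms. Equal proportional loss lowers both rates and the absolute difference but favours neither arm.

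The point is worth acting on because it touches the window of a primary safety endpoint and is cheap to close.

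**What to change.** Align the collection documents with the endpoint. State in Sections 7.3 and 8.1 that the diary starts on Day 0 after the participant leaves the clinic and continues through Day 3. Make the diary card match, and say in 8.2 and 8.5 that the rest of Day 0 is included. Add a time point for Day 0 after 30 minutes to TREF 3.2, 3.6 and 3.11, and check that the day-count categories in TREF 3.8 and 3.13 fit a four-day window. The cost is one more diary entry per participant, with the matching field and table time point. No visit is added, because staff already issue and explain the card on Day 0.

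If Day 0 after 30 minutes is left out on purpose, restate the endpoint as 30 minutes plus Day 1-3 in the Protocol Summary, Sections 3, 11.3.2 and 11.4 and the SAP synopsis, and correct Section 4.1 and Table 2 to match. This costs only wording, but the endpoint then no longer covers the rest of the vaccination day. Once cards have been completed with the later start, only this second route remains.
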